## 7.0 CLINICAL AND LABORATORY EVALUATIONS

- 7.1 Pre-treatment Evaluations
- 7.1.1 Within 8 weeks of signing informed consent:
- All the participants must have signed a consent form agreeing to participate in the study.
- Radiographic examination shall include CNS MRI (brain, cervical and thoracic spine, and saggital T1 post contrast view of the lumbar spine performed in same study and at same time as MRI of cervical and thoracic spine MRI) and CT scans of the chest and abdomen if evaluable lesions exist in these regions. MRI of the abdomen is allowed instead of CT. Appropriate additional studies should be obtained to fully define the extent and severity of existing or suspected VHL disease. Retinal examination will be performed for those patients with known or suspected retinal involvement.
- An electrocardiogram (ECG) will be completed to evaluate heart health.
- Those with a known pheochromocytoma should have serum or urinary evaluation for metanephrines and be under the care of an endocrinologist for management for changes in blood pressure at initiation of therapy

Protocol 2011-0465 ASeptember 6, 2017 Page 34 of 50

- 7.1.2 Within two weeks of study entry:
  - All patients must undergo a complete history and physical examination including vital signs, ECOG performance status, height, and current weight. Concurrent non-VHL disease and medical therapy must be documented. On-study forms must be filled out completely. All prior anti-VHL treatment must be recorded in proper detail. Laboratory studies shall include CBC w/differential, platelet count, chemistry panel (albumin, alkaline phosphatase, BUN, calcium, creatinine, glucose, LDH, phosphorus, Liver Function Test (total bilirubin, SGOT[AST] and/or SGPT[ALT]), sodium, potassium, carbon dioxide, chloride, lipase, PT, PTT. Urine protein creatinine ratio. Serum pregnancy test in female patients of childbearing potential (not postmenopausal for at least one year or not surgically capable of bearing children) will also be included.
  - Optional baseline blood will be collected for correlative studies (approximately 30cc).
  - Any residual toxicity from prior therapies should be recorded by using the grading schema in NCI Common Toxicity Criteria v4.0.
  - 7.2 Evaluation During Treatment
- 7.2.1 On-study evaluations will consist of the following study activities. A cycle is considered a 4 week period of treatment. Labs that are not drawn at the time of a visit or restaging can be obtained at a medical facility or laboratory that is not directly associated with the Investigator's institution, and forwarded to the Investigator within 96 hours (4 days).
  - Liver Function Test (Serum total bilirubin, SGOT[AST], SGPT [ALT]), will be drawn every two weeks for the first eight weeks (+/- 3 days), and then at the beginning of every cycle (+/- 3 days).
  - Serum chemistry and electrolytes including albumin, alkaline phosphatase, BUN, calcium, creatinine, glucose, LDH, phosphorus, total protein, sodium, potassium, carbon dioxide, chloride, lipase, are to be done at the beginning of every cycle (4 weeks +/- 3 days). Hematology including CBC with differential and platelet counts at the beginning of every cycle (4 weeks +/- 3 days).

• Interim medical history and physical examination (including vital signs and weight) every 12 weeks (+/- 7 days), at the time of restaging (physical examination will only be repeated at C1D1 if > 7 days since screening).

• ECOG performance status with each Physical Exam.

• Record concomitant medications at the time of interim medical history and physical exam (which will be done every 12 weeks +/- 7days). Monitor for adverse events.

Protocol 2011-0465 ASeptember 6, 2017 Page 35 of 50

• Repeat radiographic examination (CT, MRI, as indicated) to evaluate disease progression or response will be done at the end of cycles 3 and 6, and will coincide with interim medical history and physical examination, and every 12 weeks thereafter (if patient continues on treatment) (+/- 7days).

• Retinal examination for those with known retinal lesions at the end of cycles 3 and 6 +/- 7 days.

• Optional blood for correlative studies will be drawn while receiving study drug after 12 weeks +/- 1 week and after 24 weeks +/- 1 week to coincide with the restaging visits.

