## **3.0 PATIENT SELECTION**

- 3.1 Inclusion Criteria
  - 1. Subjects must provide written informed consent prior to performance of study-specific procedures or assessments, and must be willing to comply with treatment and follow-up. Procedures conducted as part of the subject's routine clinical management (e.g., blood count, imaging study) and obtained prior to signing of informed consent may be utilized for screening or baseline purposes provided these procedures are conducted as specified in the protocol.
  - 2. Eastern Cooperative Oncology Group (ECOG) performance status of  $\leq 2$ .
  - 3. Genetically confirmed diagnosis of VHL or measurable disease consistent with the clinical diagnosis of VHL. (Please refer to criterion #5)

Protocol 2011-0465 ASeptember 6, 2017 Page 14 of 50

- 4. Measurable disease criteria:
  - At least one measurable VHL related lesion, which is undergoing surveillance, and patient is not at immediate risk of needing intervention for this or other lesions. Biopsy is not required given the known likely etiology and natural history in the setting of a positive genetic test.
    - a. Brain: asymptomatic hemangioblastoma,  $\geq 0.5$  cm
    - b. Spine: asymptomatic hemangioblastoma,  $\geq 0.5$  cm
    - c. Renal: solid mass suspicious for RCC ≥1 cm or cystic mass (Bosniak 3-4) ≥1 cm.
    - d. Pancreas: solid mass  $\geq 1$  cm and  $\leq 3$  cm suspicious for neuroendocrine tumor, or neuroendocrine tumor > 3 cm but not considered operable.
    - e. Eye: asymptomatic peripapillary and/or macular hemangioblastoma, any size
    - f. Adrenal: asymptomatic or controlled pheochromocytoma greater than 1cm in size
- 5. Patients may have received prior VHL-related systemic therapy, provided not within 14 days or five half-lives of a drug (whichever is longer) prior to the first dose of pazopanib.

Protocol 2011-0465 ASeptember 6, 2017 Page 15 of 50

6. Adequate organ-system function as defined in Table 4.

System	Laboratory Values
Hematologic	
Absolute neutrophil count	$\geq 1.5 \text{ X } 10^{9}/\text{L}$
(ANC)	
Hemoglobin a	$\geq 9 \text{ g/dL} (5.6 \text{ mmol/L})$
Platelets	≥100 X 10  /L
Prothrombin time (PT) or	≤1.2 X ULN
international normalized ratio (INR) b	
Activated partial thromboplastin	≤1.2 X ULN
time (aPTT)	
Hepatic	
Total bilirubin	≤1.5 X ULN
Alanine amino transferase	≤2.0 X ULN
(ALT) and Aspartate	
aminotransferase (AST) c	
Renal	

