- 9. Prior major surgery or trauma within 28 days prior to first dose of study drug and/or presence of any non-healing wound, fracture, or ulcer (procedures such as catheter placement not considered to be major).
- 10. Evidence of active bleeding or bleeding diathesis.
- 11. Any serious and/or unstable pre-existing medical, psychiatric, or other condition that could interfere with subject's safety, provision of informed consent, or compliance to study procedures.

Protocol 2011-0465 ASeptember 6, 2017 Page 18 of 50

- 12. Unable or unwilling to discontinue use of prohibited medications list in Section 4.0 for at least 14 days or five half-lives of a drug (whichever is longer) prior to the first dose of study drug and for the duration of the study (Section 5.0).
- 13. Treatment with any of the following anti-cancer therapies:
  - 1. radiation therapy, surgery or tumor embolization within 14 days prior to the first dose of pazopanib OR
  - 2. chemotherapy, immunotherapy, biologic therapy, investigational therapy or hormonal therapy within 14 days or five half-lives of a drug (whichever is longer) prior to the first dose of pazopanib
- 14. Any ongoing toxicity from prior investigational therapy that is >Grade 1 and/or that is progressing in severity, except alopecia.
- 3.3 Inclusion of Women and Minorities

Both men and women and members of all races and ethnic groups are eligible for this trial.

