#### **Prohibited Medications**

Subjects should not receive other investigational therapy while on treatment in this study. The time period that subjects should not receive any other investigational drugs prior to the first dose of study drug is 28 days. Subjects should not receive any other investigational drug within 15 days of the last dose of pazopanib and until post-treatment blood draws are completed.

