#### 7.5 Study Calendar

Baseline evaluations are to be conducted within 2 weeks prior to study entry. Scans must be done within 8 weeks of signing the informed consent. In the event that the patient's condition is deteriorating, laboratory evaluations should be repeated within 48 hours prior to initiation of the next cycle of therapy. Cycle 1 physical examination will only have to be repeated in > 7 days from screening.

		Cycle 1	Cycle 2	Cycle 3	Cycle 4	Cycle 5	Cycle 6	Additional Cycles	
	Baseline	Wk 1-4	Wk 5-8	Wk 9-12	Wk 13-16	Wk 17-20	Wk 21-24		Early Withdrawal/Post- Treatment Evaluation d
Pazopanib		Х	Х	Х	Х	Х	Х	Х	
Informed Consent	Х								
History and Physical 	Xj	Х			Х			X m	Х
Concomitant Medications	Х	Х			Х		Х	Х	Х
Performance Status	Х	Х			Х			X m	Х
CBC w/diff, plts	Х	Х	Х	Х	Х	Х	Х	Х	Х
Serum Chemistry b	X k	Х	Х	Х	Х	Х	Х	Х	Х
Protocol 2011-0465 ASeptember 6, 2017 Page 37 of 50

UPRC	Х								
EKG	Х								
Liver Function Tests i	Х	Х	Х	Х	Х	Х	Х	Х	Х
B-HCG	Xc								
Optional Blood for Correlative Studies g	Х			X			Х	Х	Xf
Radiographic and Retinal Examination e,h	Х				Х		Х	Х	Х
Adverse Event Monitoring	X	←					→	Х	Х

a: Pazopanib Dose as assigned; route/schedule.

b: Albumin, alkaline phosphatase, BUN, calcium, creatinine, glucose, LDH, phosphorus, total protein, sodium, potassium, carbon dioxide, chloride, lipase. Note: Add PT and PTT testing at screening only.

c: Serum pregnancy test (women of childbearing potential).

d: Off-study evaluation may take place within 5-7 months after the last dose of study drug.

e. If high-quality baseline measurement is available from an outside institution, this will be considered acceptable. For individuals who do not have retinal lesions, no further retinal evaluations will be necessary for study purposes. If retinal lesions are present, retinal exams must take place every 12 weeks (+/- 7 days)

f. A single sample (approximately 10 cc) at treatment discontinuation (only if related to disease progression).

g. Optional blood also drawn at time of dose reduction or modification

h. Follow-up radiographic scans will take place at the end of cycles 3 and 6, and every 12 weeks thereafter (+/- 7 days).

i. Liver function tests (LFTs) are defined as total bilirubin, SGPT (ALT) and SGOT (AST). For the first eight weeks of study, LFTs will be drawn EVERY TWO WEEKS and every four weeks thereafter.

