### 9.0 CORRELATIVE/SPECIAL STUDIES

- 9.1 Correlate responders/nonresponders with genetic mutation analysis in order to define genetic signatures of responses at the organ level.
- 9.2 Baseline, week 12 and week 24 blood will be drawn and processed for cytokineangiogenesis factor analysis. A 50 panel Luminex bead based assay will be employed to evaluate baseline and therapy-induced changes in the profile. This profile will also be compared to internally generated data on patients with sporadic RCC to further explore the disease and therapy specificity of the profile.

9.3 Baseline, week 12 and week 24 blood will be drawn to evaluate baseline circulating endothelial cells and their changes as a function of therapy. These exploratory data will be employed to generate hypotheses on the interaction between host, tumor and therapy.

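### The baseline correlative blood is timed to study entry and the washout of prior therapy to the first dose, so in recently pretreated patients the baseline marker sample can carry residual prior-drug effect

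*Combined protocol and SAP*

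**What the plan says.** **The draw.** The protocol provides for the sample with the words "Optional baseline blood will be collected for correlative studies (approximately 30cc"), listed under the item "7.1.2 Within two weeks of study entry", and the Study Calendar (7.5) states "Baseline evaluations are to be conducted within 2 weeks prior to study entry". Study entry is not defined, and its distance from the first dose is not limited. Section 7.2.1 allows for a gap between screening and treatment: "physical examination will only be repeated at C1D1 if > 7 days since screening".

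**The washout.** Section 3.1, item 5 admits patients with earlier systemic VHL therapy, "provided not within 14 days or five half-lives of a drug (whichever is longer) prior to the first dose of pazopanib". Section 3.2, item 13 uses the same length and the same anchor for "chemotherapy, immunotherapy, biologic therapy, investigational therapy or hormonal therapy within 14 days or five half-lives of a drug". For investigational drugs, the Prohibited Medications text in section 4 sets a different limit: the drug-free period "prior to the first dose of study drug is 28 days".

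**The use.** Section 9.2 uses baseline, week 12 and week 24 blood to "evaluate baseline and therapy-induced changes in the profile" and to compare the profile with sporadic RCC. Section 9.3 does the same for circulating endothelial cells and calls those data exploratory. Section 2.6 asks whether baseline factors predict benefit. Section 12.2 plans mixed models for marker change and tests of marker against response, and does not mention adjustment for prior therapy. The calendar has no pre-dose Cycle 1 Day 1 correlative sample.

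**The concern.** The draw and the washout run on two different clocks, and no section connects them. A patient can satisfy every eligibility rule on the day of first dose and still have given the baseline sample while the washout was in progress.

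The protocol itself makes prior VEGF-pathway treatment conceivable. Section 2.3 names several such agents and describes the same group's sunitinib trial in VHL. Section 2.2 reports that pazopanib exposure is related to the fall in a circulating receptor, sVEGFR2, so drugs of this kind can move blood markers.

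If the earlier drug moves a marker in the same direction as pazopanib, a sample that still carries its effect makes the pazopanib-induced change look smaller. It also ties the baseline level to treatment history, which confounds the tests of baseline marker against response and the comparison with sporadic RCC.

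**Working it through.** The plan gives no effect size, alpha or power for the markers, so there is no figure to reproduce. The check is date arithmetic followed by an illustrative power calculation.

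**Inputs from the protocol**
- Draw window: up to 14 days before study entry (7.1.2, 7.5).
- Washout: W = max(14, 5T) days before first dose, where T is the half-life in days (3.1 item 5; 3.2 item 13).
- Gap g from study entry to first dose: not given.

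**Step 1. Time from last prior dose to draw.** The earliest draw is day -(14 + g), and the last permitted prior dose is about day -W. The interval is W - (14 + g) days, and residual drug is 2^(-interval/T).

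**Step 2. Study entry on the day of first dose (g = 0), draw on day -14.** For T up to 2.8 days, 5T ≤ 14, so W = 14. The eligibility wording excludes dosing within 14 days, so I take the last prior dose as day -15, one day before the draw. For longer half-lives I take it at exactly five half-lives.

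| Half-life T (days) | Last prior dose | Days to draw | Residual at draw |
|---|---|---|---|
| 1 | day -15 | 1 | 2^(-1) = 50% |
| 2 | day -15 | 1 | 2^(-1/2) = 71% |
| 2.8 | day -15 | 1 | 2^(-1/2.8) = 78% |
| 4 | day -20 | 6 | 2^(-6/4) = 35% |
| 5 | day -25 | 11 | 2^(-11/5) = 22% |
| 7 | day -35 | 21 | 2^(-3) = 12.5% |

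Moving the last dose one further day back in the longer-half-life rows gives 2^(-7/4) = 30% at 4 days and 2^(-22/7) = 11% at 7 days. Once washout is complete, at least five half-lives have passed and the residual is at most 2^(-5) = 3.1%.

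**Step 3. Study entry before first dose (g > 0).** The earliest draw moves back by g days and the washout does not. For T up to 2.8 days, a gap of one day lets the draw reach the last day of prior dosing, and a longer gap lets it fall earlier. With g = 7 and T = 4 the interval is 20 - 21 = -1 day. With g = 14 and T = 5 it is 25 - 28 = -3 days. A negative interval means that the sample is taken during prior dosing.

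**Step 4. The 28-day limit for investigational drugs.** Where it applies, with g = 0 and a draw on day -14, the residual is 2^(-14/T) for T up to 5.6 days: at most 2^(-5) = 3.1% for T ≤ 2.8, 2^(-3.5) = 8.8% at 4 days and 2^(-2.5) = 18% at 5.6 days. Beyond 5.6 days five half-lives exceed 28 days and the table in step 2 applies.

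**Step 5. Illustrative effect on power.** Assumptions, none from the documents: true change 0.5 SD, 40 complete pairs, paired t-test at two-sided 0.05, a share p of patients sampled with a fraction r of the prior effect still present, acting in the same direction as pazopanib. Then the mean change is 0.5(1 - pr), its SD is sqrt(1 + p(1 - p)(0.5r)²), and power comes from the noncentral t with 39 df and noncentrality sqrt(40) × mean/SD.

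| p | r = 1: mean, SD | Power, r = 1 | Power, r = 0.5 |
|---|---|---|---|
| 0 | 0.500, 1.000 | 87% | 87% |
| 5% | 0.475, 1.006 | 83% | 85% |
| 10% | 0.450, 1.011 | 78% | 83% |
| 20% | 0.400, 1.020 | 68% | 79% |

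**The case against.** A reader might infer four stronger things, and the documents do not support them.

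- *That the sample is taken on the previous drug.* This requires study entry to precede first dose. The documents neither state nor exclude that. If the two coincide, the draw falls after the last prior dose.
- *That all of the prior drug remains.* This requires the last prior dose and the draw both on day -14, while item 5 excludes dosing within 14 days. Section 7.1.2 also sets a window, not a day -14 draw, so every residual above is a worst-case edge.
- *That a large share of patients is affected.* Section 3.1, item 4 selects patients whose lesion is under surveillance and who are not at immediate risk of intervention. Section 2.3 says the VEGF agents were approved for advanced RCC. Nothing in the documents supports a particular contaminated share.
- *That the trial's main conclusion is at risk.* The blood is optional and the marker work exploratory.

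Other limits also stand. Forty pairs is a ceiling. Section 12.2 plans mixed models, not a paired t-test. The sVEGFR2 finding concerns pazopanib, and the protocol does not say that this marker is in the 50-analyte panel or how quickly markers recover. Section 3.2, item 9 requires 28 days after major surgery, so recent major surgery adds little to the concern. Prior VHL treatment must be recorded in detail, so affected samples could be identified afterwards.

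These points limit the reach and size of the problem. They do not connect the two clocks, and no section plans to use the prior-treatment record in the marker analyses.

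**Conclusion.** The point holds as a possible bias in the exploratory analyses of change from baseline and of marker against response, confined to patients with recent prior systemic therapy. The residual figures rest on a draw at the edge of the window and describe drug level, not marker effect. The power figures depend on an assumed effect, an assumed share and a same-direction prior effect, and show sensitivity rather than an expected loss. With 5 to 10% of samples affected the loss is 4 to 9 percentage points at full prior effect and 2 to 4 at half effect. The response-rate endpoint and the progression and discontinuation stopping rules are unaffected. This is a cheap improvement worth making, not a flaw in the main design.

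**What to change.** In 7.1.2 and the calendar, state that the baseline correlative blood is drawn after the washout of prior therapy is complete and before the first pazopanib dose, for example pre-dose on Cycle 1 Day 1. For an eligible patient that timing meets both conditions, because the washout is counted to the first dose. The words pre-dose and after washout need to be explicit: the cycle-start labs carry a window of ±3 days and may be drawn at outside laboratories (7.2.1).

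For samples already taken, use the recorded prior-therapy dates to restrict or stratify the 9.2 and 9.3 analyses by time since last prior therapy, and add this to 12.2.

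The differing limits for prior investigational therapy in section 3.2, item 13 and in Prohibited Medications must be reconciled, since they decide how much residual drug is possible for those patients.

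Cost: a short wording change and one added line of analysis. The draw must be on site and pre-dose, so it may not always coincide with the Cycle 1 labs and may sometimes need a separate collection. Patients who consent but never start treatment would give no sample, but they do not enter a change-from-baseline analysis.

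### Urine protein is scheduled at baseline only, and the first informative on-treatment blood pressure probably falls at week 12, although Table 5 acts on both measurements

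*Combined protocol and SAP*

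**What the plan says.** **Action rules.** Section 6.1 introduces Table 5 as recommendations. For proteinuria, it advises interrupting pazopanib at UPC ≥3 or 24-hour urine protein ≥3 g, with weekly urine monitoring from that point. Below 3 it leaves monitoring to clinical judgement. For hypertension, scenario A covers asymptomatic, persistent systolic pressure of 140 to below 170 mmHg or diastolic pressure of 90 to below 110 mmHg. Scenario B covers asymptomatic pressure of 170/110 or above, or failure of control under A.

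**Urine protein schedule.** Section 7.1.2 lists "Urine protein creatinine ratio" among the tests within two weeks of study entry. In the Section 7.5 calendar that row has one mark, at Baseline. Section 7.2.1 opens with "On-study evaluations will consist of the following study activities"; its list covers liver tests, chemistry, hematology, examinations, imaging and optional blood, but no urine test. The end-of-treatment list in Section 7.2.2 has none either. Section 7.3 carries the same schedule into continued treatment.

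**Blood pressure schedule.** Section 7.2.1 asks for "Interim medical history and physical examination (including vital signs and weight) every 12 weeks", at restaging, with a window of 7 days. The Cycle 1 Day 1 examination is repeated only if more than 7 days have passed since screening. In the calendar, the History and Physical row is marked at Baseline, Cycle 1 and Cycle 4, for additional cycles and post-treatment. The footnote on that row, however, refers to the first day of every cycle and says that vital signs are taken at the physical examination.

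**Liver tests, for contrast.** These "will be drawn every two weeks for the first eight weeks" and then at the start of each cycle.

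**The concern.** An action rule works only if someone takes the measurement that triggers it. Proteinuria is usually silent, and scenarios A and B of Table 5 are defined by asymptomatic pressure, so asking patients about symptoms cannot start either pathway. The weekly urine monitoring in Table 5 does not help with the first event, because it begins only once a value of 3 or more is known.

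This is a patient-safety point. Section 2.2 places hypertension among the most frequent Grade 3 or 4 events, relates its development to pazopanib trough concentration, and says that the protocol is designed to monitor such class effects closely. The protocol also foresees pressure changes early in treatment, but only for patients with known pheochromocytoma, who are to be "under the care of an endocrinologist for management for changes in blood pressure at initiation of therapy". For everyone else, if the 12-weekly text is followed, asymptomatic hypertension in the first 11 to 13 weeks may come to light only through an unscheduled reading. The same holds for silent proteinuria at any time on drug. The step that Table 5 recommends could then come late or not at all.

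**Working it through.** The plan states no figure on this point, so there is none to reproduce. The check sets the schedule beside the action rules and counts dates, with a 4-week cycle (Section 7.2.1). Counts run from after Cycle 1 Day 1 through week 24. The Cycle 1 Day 1 examination is left out because, if done at all, it is assumed to precede drug exposure.

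**Step 1. UPC as planned.** Sections 7.2.1 and 7.2.2 list none, and the calendar marks Baseline only. Scheduled on-treatment tests = 0 on any reading.

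**Step 2. BP as planned.**
- Reading A (12-weekly text of Section 7.2.1): weeks 12 and 24 = 2 readings. First reading at day 84 ± 7, that is days 77 to 91, or weeks 11 to 13.
- Reading B (row footnote taken as every cycle): starts of Cycles 2 to 6 = weeks 4, 8, 12, 16 and 20, plus the week 24 restaging examination = 6 readings. First reading at week 4.

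Reading A is the more probable. The body text gives the 12-week interval for the examination twice, and the calendar leaves Cycles 2 and 3 blank. The marks are not clean evidence, though: Cycle 6 is also blank, although Section 7.2.1 puts an examination at its end.

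**Step 3. Dates already in use.** Liver tests: weeks 2, 4, 6 and 8, then the starts of Cycles 4, 5 and 6 = weeks 12, 16 and 20, so 7 dates. Adding week 24 restaging gives 8.

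**Step 4. Counts with the fix, if all 40 patients complete 24 weeks.**

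| Item | Per patient now | Per patient with fix | Added across 40 patients |
|---|---|---|---|
| UPC at weeks 12 and 24 | 0 | 2 | 2 × 40 = 80 |
| UPC each cycle plus week 24 (optional) | 0 | 6 | 6 × 40 = 240 |
| BP, reading A | 2 | 8 | (8 − 2) × 40 = 240 |
| BP, reading B | 6 | 8 | (8 − 6) × 40 = 80 |

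These are upper bounds, because patients who stop early need fewer. A separate end-of-treatment urine sample is not counted.

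**The case against.** **Other safeguards exist.** Chemistry is drawn every cycle ("Serum chemistry and electrolytes including albumin, alkaline phosphatase, BUN, calcium, creatinine" and more, including total protein). Adverse events are monitored throughout. Table 5 asks for monitoring as clinically indicated while UPC is below 3. Drug is dispensed each cycle. Entry requires BP below 140/90 and UPC below 1, or 24-hour protein below 1 g. These reduce the risk, but none schedules a UPC or an early BP reading, and Table 5 attaches no proteinuria action to albumin or creatinine.

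**The BP gap may be small.** If the row footnote governs, BP is already 4-weekly and only weeks 2 and 6 are new. This stands as a real uncertainty. It does not remove the need to settle which text applies, and it does not touch UPC.

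**The proposed intervals are a preference.** This stands. The documents set no interval, and proteinuria is listed as less common, so UPC at the restaging visits is a sufficient minimum.

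Three stronger readings are tempting, and the documents do not support them:
- A reader might compare the 12-week gap with the 2-week period in scenario A and conclude that a monitoring rule is missed several times over. That period is for titration after hypertension has been found; it is not a measurement interval.
- A reader might conclude from the calendar footnote that allows an off-study evaluation 5 to 7 months after the last dose that no timely final BP is taken. Section 7.2.2 already requires a physical examination at the end of treatment, and the row footnote places vital signs within the examination. Only UPC is missing there.
- A reader might take Section 8.3, which holds drug for related toxicity above grade 2 and names hypertension, as a duty to detect silent events. That section concerns persistent and refractory toxicity and sets no test.

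**Conclusion.** The point holds. For UPC it is firm: 0 scheduled on-treatment tests on any reading, against a recommendation to interrupt at 3. For BP it is probable: the first informative scheduled reading is at about week 12 (11 to 13) under Section 7.2.1, or at week 4 if the row footnote governs. The two texts conflict in either case.

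This is a worthwhile, low-cost safety improvement. It is not evidence that patients were harmed. The documents give no rate for hypertension or proteinuria, so no number of missed events is claimed. Nor does anything here change the sample size or the stopping boundaries in Section 12.1. A reader might infer that the count of discontinuations for toxicity will be biased downwards. Toxicity that nobody measures cannot lead to discontinuation, but the documents give no basis for saying how often that would happen.

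A reader might also extend the point to the ECG, which is scheduled before treatment only ("An electrocardiogram (ECG) will be completed to evaluate heart health") while Table 5 discontinues at QTc ≥500 msec. The pattern is the same, but no QTc event rate is given and no on-treatment ECG is proposed here.

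The conclusion assumes that staff follow the written schedule, and that the Cycle 1 Day 1 examination cannot show a drug effect.

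**What to change.** Amend Sections 7.2.1 and 7.2.2 and the Section 7.5 calendar.

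1. **UPC.** Add it at least at the week 12 and week 24 restaging visits, every 12 weeks thereafter, and at end of treatment in Section 7.2.2. Testing each cycle is an option, not a requirement.
2. **BP.** Add readings on existing early laboratory dates, for example every 2 weeks to week 8 and then each cycle. Allow off-site or home readings explicitly. The current allowance, under which tests "can be obtained at a medical facility or laboratory that is not directly associated with" the investigator's institution, covers laboratory work only.
3. **Calendar.** Reconcile the History and Physical footnote with the 12-weekly text in Section 7.2.1.

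The cost is one amendment, at most 80 urine tests through week 24 (240 with the per-cycle option, and in either case before any separate end-of-treatment sample), and 80 to 240 extra BP readings across 40 patients. The readings fall on dates already scheduled for a draw or restaging, so no visit date is added. They still have to be collected, transmitted and reviewed, and home readings need equipment and instruction. The intervals are a matter of judgement, chosen because those dates are already in use.
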